The Tolerable Upper Limit (UL) (highest level of daily intake of calcium from food, water and supplements that is likely to not pose any risks of adverse health effects for almost all of the general population) is currently established as greater than 2,500 mg per day. Risks of intake above the UL include hypercalcemia, impaired kidney function and decreased absorption of other minerals (iron, zinc, magnesium and phosphorus). Dietary intake of calcium will be monitored at baseline with the National Osteoporosis Foundation (NOF) Calcium Intake Estimate tool, and supplements will be prescribed to ensure subjects obtain approximately 1200 mg of total calcium (diet and supplements) daily which is well below the UL. In addition, serum calcium levels will be drawn at baseline. Kidney stones have occurred with high intakes of calcium, therefore, a daily fluid intake of at least 2,000 ccs will be encouraged. Participant will be counseled verbally and in writing not to take additional supplements of calcium beyond the study protocol to keep their intake below the UL.

Risk of Vitamin D supplementation.

Excessive amounts of vitamin D (D) can result in hypercalcemia. The current Recommended Daily Amount of D is 400-800 IU/day (or 2,800 to 5,600 per week), but studies have reported that D supplements of 4,000 IU per day are safe. In addition, subjects will be monitored for signs of D toxicity, i.e. hypercalcemia (nausea, vomiting, poor appetite, constipation, weakness and weight loss) at RPC visits throughout the study. At baseline, subjects will be prescribed optimal doses of D based on the

following protocol: Subjects who have serum D levels at 30 ng/ml or greater will be prescribed 1,000 IU daily; subjects with levels of 20-29 ng/ml will be prescribed 2,000 IU daily; and subjects with levels of 10-19 ng/ml will be prescribed 3,000 IU daily. Subjects receiving 3,000 IU daily will have their serum levels rechecked at 3 months. Subjects with serum D level \geq 60 ng/ml at screening will have levels rechecked at 3 months, as well as calcium and albumin (calcium adjusted for albumin). All other subjects will have follow-up serum levels at 6 months.

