4 STUDY DESIGN

This study has a stratified, randomized 3-group (2 treatment groups & 1 control group), repeated measures experimental design. A computer generated code will be used for randomization to 3 groups (Control: n =103; Risedronate: n =103; Exercise: n =103) with assignments placed in sealed opaque envelopes for sequential use. All subjects will take dosages of calcium citrate supplements sufficient to ensure their total daily calcium (diet+supplements) is ~ 1200 mg daily and vitamin D³ supplements with daily dose to ensure serum levels of vitamin D [25 (OH)D] are between 30 ng/mL and 80 ng/mL(optimal CaD). Subjects randomized to the Risedronate group will take optimal CaD daily and 150mg of oral risedronate once monthly for 12 months but will not participate in the exercise program. Subjects randomized to the Exercise group will take optimal CaD and also participate in 12 months of a bone-loading exercise program three times weekly at a local community-based Y. To ensure the bone outcomes were not due to the CaD supplementation, a group taking only optimal CaD will serve as a control. We believe it would be unethical for women at risk for further bone loss to have restrictions in physical activity for 12 months. Thus, while only women in the exercise group will participate in the structured bone-loading exercise program developed for this study, all women will be encouraged to participate in exercises and will be informed of the benefit of weight bearing and resistance exercises. **The primary outcome will be bone structure at the tibia and hip and secondary outcomes are BMD and bone turnover.** Repeated measures of primary and secondary outcome variables will be conducted at baseline, 6 and 12 months to better understand response to intervention components with a maximum difference expected at 12 months. An exercise intervention lasting 12 months or 2 to 3 bone turnover (resorption / formation) cycles is necessary in order to measure the effects of training on bone outcome

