6.3 Intervention Fidelity and Assessment of Compliance

Low adherence rates to exercises, risedronate, and CaD would impact fidelity of intervention components and limit generalizability of study results.

According to Bandura, adherence is related to "task and barrier self-efficacy". Task self-efficacy is subject's confidence in their ability to perform interventions such as exercises, and barrier self-efficacy is subjects confidence in their ability to overcome barriers to interventions. We will promote task and barrier self-efficacy through subject education, goal setting, reducing barriers, and by providing graphic feedback on goal achievements.

Feedback sheets will be provided to subjects to demonstrate progress over time in adherence to interventions, 1RM measures, weight loads for exercises, and BMD. Scripts will be provided for assisting with goal-setting and reducing barriers to promote standardization across sites. Strategies for reducing barriers to adherence to exercises will be tailored to subjects based on their scores on the Barriers Interference instrument.

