6.4.4 Enrollment/Baseline

To print the forms needed for an enrollment visit, see *Packet 3. Enrollment Visit Forms*. All other forms needed for this visit are in RedCap. Checklists for this visit are printed and available at the ORC.

1. Complete process of informed consent to the Main Study (see *Form 34. Main Study Consent*; see *Protocol 39. Main Study Consent Guidelines for Completion*.)
2. Randomization: Open the next envelope (envelope on the “top” of the pile located in desk in HOPS office at ORC) and read treatment group out loud.
3. Select the appropriate checklist (see *Form 35. Enrollment Checklist Exercise*, *Form 36. Enrollment Checklist Control*, *Form 37. Enrollment Checklist Risedronate*)
4. Participant will complete *Form 43. NOF Calcium Intake Estimate_Revised* using paper and pencil (see *Protocol 40. NOF Calcium Intake Calculator*)
5. Walk the participant down to the ORC, where they will complete the PQCT. Leave study Checklist with the participant, so that the ORC personnel can initial that the Pqct has been completed. This scan takes approximately 5 minutes.
6. During pQCT:
 1. Open RedCap complete the ID# assignment using *Protocol 24. RedCap Data Entry* (see also *Packet 4. Control Group_All Enrollment Forms*, *Packet 5. Risedronate Group_All Enrollment Forms*, *Packet 6. Exercise Group_All Enrollment Forms*, if you are using hard copy questionnaires).
 2. Locate appropriate Participant Manual (see *Packet 7. Control Group_Participant Manual*, *Packet 8. Risedronate Group_Participant Manual*, *Packet 9. Exercise Group_Participant Manual*). These are located in the ORC, although personnel will need to print copies of these periodically.

Control Group Protocol:

1. Participant Manual will contain the following:
 - a. *Form 15. One Page Study Summary_3*
 - b. *Form 38. What is Osteoporosis*
 - c. *Form 39. Exercise and Your Bones*
 - d. *Form 40. Instructions for Calcium and Vitamin D*
 - e. *Form 1. Calendar Card Instructions*
 - f. *Form 41. Lexicomp Online Patient Education Cholecalciferol*
 - g. *Form 42. Lexicomp Online Patient Education Calcium Citrate*
2. Participant will complete the *Form 44. Health History Form* in RedCap
3. Research Project coordinator will educate participant on CaD referencing *Form 45. Instructions for Calcium and Vitamin D Usage* and using *Protocol 42. Administering Edu CaD* as a guide.

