The relationships of interest in Aim 4 will be explored by assessing the correlations between percentage of sessions attended, percentage of risedronate pills taken, and 12-month changes in bone structure at the tibia and hip. Assuming the variables are normally distributed, Pearson correlations will be used. Spearman rank correlations will be used if any of the variables are found to be non-normal.

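### The calcium self-report that sets each woman's supplement is taken after her group is announced, which leaves calcium prescribing open to avoidable differences by arm

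*Combined protocol and SAP*

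**What the plan says.** Section 4 gives the CaD-only arm its purpose: "To ensure the bone outcomes were not due to the CaD supplementation, a group taking only optimal CaD will serve as a control". Section 6.1 repeats this.

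Section 2.3.1 describes how calcium is set. On intake: "Dietary intake of calcium will be monitored at baseline with the National Osteoporosis Foundation (NOF) Calcium Intake Estimate tool". On the supplement: "supplements will be prescribed to ensure subjects obtain approximately 1200 mg of total calcium (diet and supplements) daily". The target is the same in all arms.

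Section 6.4.4 gives the order of the enrollment visit. Step 1 is main-study consent. At step 2 staff open the next envelope "and read treatment group out loud". At step 4 comes the dietary-calcium form: "Participant will complete *Form 43. NOF Calcium Intake Estimate_Revised* using paper and pencil". Form 43 then appears again in the Risedronate list and the Exercise list, but not in the Control list. In every arm the research project coordinator then prescribes calcium and vitamin D on Form 49.

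Vitamin D is handled differently. Section 6.2 assigns its dose by serum 25(OH)D band under one rule for all three groups, and section 6.4.3 lists serum vitamin D among the screening blood tests, before randomization.

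On adherence, section 6.3 warns: "Low adherence rates to exercises, risedronate, and CaD would impact fidelity of intervention components". Section 6.2 has supplement cards collected every four weeks and allows women to use their own supplements under monitoring. Section 7.2.1 lists serum vitamin D at 6 months. In section 10.3 the adherence variables are "percentage of sessions attended, percentage of risedronate pills taken"; no CaD variable appears.

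**The concern.** A background treatment shared by all arms should be fixed from information gathered before anyone knows the allocation. Here the only input to the calcium dose described in the text is a self-report made once both the woman and the coordinator know her group. The blinding in section 6.1 covers the assessors of outcomes, not these two people. Two arms are also listed as completing the form twice, and the text does not say which report would govern the prescription.

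If reported intake or prescribing differed by arm, part of an Exercise–Control or Risedronate–Control difference in bone structure, BMD or turnover could be due to calcium and be credited to the exercise or the drug. The CaD-only arm was included to prevent that attribution. The protocol does not regard CaD as inert: section 2.2 says it does better than no treatment, and that earlier data suggest bisphosphonates and exercise both work better with optimal CaD.

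**Working it through.** **1. The plan's own figure.** Section 10.2 gives 82 per group (246 in all) for 80% power. Inputs: two groups, three time points, f = 0.10, correlation 0.5, alpha 0.05. For the interaction test with 164 women, the noncentrality is 164 × 3 × 0.10² / (1 − 0.5) = 9.84, on 2 and (164 − 2) × 2 = 324 degrees of freedom. Power is 80.5%, and 164 × 1.5 = 246, so the figure reproduces. With 20% attrition, 82/0.8 = 102.5, rounded up to 103 per arm, or 309. These figures neither support nor weaken the point; 82 per arm is used below.

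**2. Which inputs come before allocation.**

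| Input | Source | Timing against envelope | Exposed? |
|---|---|---|---|
| Vitamin D dose | Screening serum (6.2, 6.4.3) | Before | No |
| Reported dietary calcium | Form 43 (6.4.4, step 4) | After | Yes |
| Second Form 43 | Risedronate and Exercise lists only (6.4.4) | After | Yes, and unequal by arm |
| Calcium prescription | Form 49, by a coordinator who knows the arm (6.4.4) | After | Yes |

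**3. How a reporting difference would carry through.** Let T be true dietary calcium and R reported calcium, in mg a day. Treating the top-up as exact and R as below 1200:

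- supplement = 1200 − R
- total calcium if the supplement is taken in full = T + 1200 − R = 1200 + (T − R)

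Randomization balances T in expectation. The expected arm difference in total calcium is therefore the arm difference in mean reporting error, T − R. Misreporting of the same size in every arm cancels. A 100 mg shift in R moves the supplement by 100 mg, and 100/1200 = 8.3% of the target. In practice the supplement comes as tablets of unstated strength toward an approximate target, so a 100 mg shift might change nothing or might change a whole tablet.

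**4. Size of the effect on bone.** The documents give neither an arm difference in calcium nor a bone effect per mg. For illustration only, assume a calcium imbalance makes two arms diverge linearly by D SD at 12 months with no true intervention effect. Then f = D/√24, and f = 0.10 corresponds to D = 0.49. At 82 per arm, the chance of a significant time-by-group test is:

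| D (SD) | 0.05 | 0.10 | 0.20 | 0.30 | 0.49 |
|---|---|---|---|---|---|
| Chance | 5.8% | 8.2% | 19.0% | 38.4% | 80.5% |

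Nothing in the documents says which D, if any, applies. At the low end the rate is barely above the nominal 5%.

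**5. What a by-arm table could show.** With 82 per arm, the standard error of a difference in SD units is √(2/82) = 0.156. The 95% CI half-width is 1.96 × 0.156 = 0.31 SD. The difference detectable with 80% power is (1.96 + 0.84) × 0.156 = 0.44 SD. A non-significant result would not establish equal exposure, so the interval is what should be reported.

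**The case against.** The strongest reply is that the trial already protects the comparison. Arms are randomized with one calcium target and one serum-based vitamin D rule, so Control removes the effect of assigned CaD. Every arm also has a 3-month review of compliance and supplement dose (study schematic), four-weekly card collection, monitoring of own supplements and a later serum vitamin D check. Section 2.3.1 has women counselled against extra supplements, and section 9 has compliance audits at least every three months. All of this stands. A reader might infer from the enrollment order that Control cannot rule out CaD, or that the plan neither protects nor checks CaD exposure; the documents support neither inference.

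Second, no mechanism is given for a woman to report a different diet because of the arm she drew. She fills in the form herself, and Protocols 40 and 41, cited for the estimate and the prescription, may leave the coordinator little discretion. This also stands: no direction of bias can be stated. Those procedures, and Protocols 1, 2 and 48–50, appear by title only, so a repeat intake measure or a fixed dosing table cannot be excluded. Neither would change the order of steps in section 6.4.4.

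Third, tablet-taking after randomization can differ by arm wherever Form 43 sits, and under intention to treat that does not invalidate the randomized contrast. True. What is at stake is attribution to exercise or drug rather than to calcium. Moving the form protects the baseline prescription only. The by-arm table alone would be a reporting addition.

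**Conclusion.** The point holds as a minor, avoidable weakness in the order of the enrollment visit. The self-report and the prescription that set the calcium supplement both follow disclosure of the group, and the self-report is listed twice in two arms and once in the third. Vitamin D dosing is not affected.

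The result is an unprotected risk of unknown and possibly small size. It becomes a bias in attribution only if reporting error or prescribing differs between arms, and the documents contain no evidence that either does. The conclusion rests on the visit being run in the order written and on the supplement being set from Form 43, as section 2.3.1 describes. The statement that CaD is not compared by arm means only that section 10.3 lists no such comparison; data for one are collected.

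**What to change.** In section 6.4.4, have every woman complete Form 43 and have the coordinator make the calcium entry on Form 49 between step 1 (main consent) and step 2 (envelope). Delete the repeat of Form 43 from the Risedronate and Exercise lists. The dosing rule does not change.

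As supporting description, add to section 10.3 a by-arm table of prescribed calcium, percentage of CaD tablets taken (from returned cards or the own-supplement calendar) and month-6 25(OH)D. Show differences from Control with 95% CIs rather than relying on significance tests, and report the table beside the Aim 1–3 contrasts.

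The cost is reordering paperwork within one visit, plus one table from data already collected. No visit, assay or participant is added. The downside is a few minutes of form time for any woman who withdraws before the envelope is opened.

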6.4.5 After Enrollment Visit

Follow the steps listed in *Protocol 45. Steps to Take After Enrollment Visit*. This will include issuing the participant's first payment. Use *Protocol 46. Issuing Participant Payment Request*, as a guide.

If the participant was assigned to the Exercise group, make sure that the items outlined in *Protocol 44. Steps to Take After Randomization to Exercise Group* have been addressed.

If the participant was randomized to the Risedronate group, follow the steps listed in *Protocol 47. Acquiring Risedronate Rx*, to attain a risedronate prescription for the participant.

6.4.6 Intermediate Visits

Subjects will have follow up contact at 2 weeks, 3M, 6M, and 12M. Additional contact will be made between exercise participants and [name], the RET. Additional contact will occur between RPCs and participants as needed. If at any time during enrollment, a participant indicates that they have suffered a fracture, the participant will be asked to complete the *Form 64. Fractures Documentation_Revised*, and the participant's provider will determine whether continuation in the study is appropriate.

See *Protocol 1. Timeline for Data Collection* for details.

7 STUDY PROCEDURES /EVALUATIONS

7.1 Study Procedures

See [Protocol 1. Timeline for Data Collection](#) for details.

[Protocol 48. Data Collection_Control Group](#), [Protocol 49. Data Collection_Risedronate Group](#), [Protocol 50. Data Collection_Exercise Group](#) for detailed data collection timelines according to treatment group.

7.2 Laboratory Procedures/Evaluations

7.2.1 Clinical Laboratory Evaluations

Screening blood tests will include:

- CBC
- Serum vitamin D
- Serum calcium
- Serum creatinine
- Parathyroid hormone
- Follicle-stimulating hormone (if applicable)
- Thyroid stimulating hormone (if applicable)
- Additional serum drawn at screening will be stored and used for baseline analysis of Alkphase B and Serum NTx (markers of bone turnover) and other factors that may affect bone health

Blood tests performed at 6 months:

- Serum vitamin D
- Alkphase B
- Serum NTx

Blood tests performed at 12 months:

- Alkphase B
- Serum NTx

7.2.2 Special Assays or Procedures

- Dual energy x-ray absorptiometry (DXA) at screening(baseline), 6M, 12M
 - Hip Structural Analysis at screening (baseline), 6M, 12M
 - Trabecular Bone Score at screening, 6M, 12M
- Peripheral quantitative computed tomography (pQCT) at baseline, 6M, 12M
- Estimated 1 repetition maximum (1 RM) at 2 weeks, 6M

7.2.3 Specimen Preparation, Handling, and Storage

Blood draws will be performed at either TNMC Clinical Research Center or at the Creighton Osteoporosis Research Center depending on subject availability and preference. Personnel will follow appropriate protocols for venipuncture and transportation of specimens (see [Protocol 32. Blood Draw Procedure](#), and [Protocol 33. Blood Transportation Protocol](#)). As indicated in [Protocol 33. Blood Transportation](#)

Protocol, some specimens will be stored in [name] lab, while others will be analyzed by the TNMC laboratory. For specimens to be aliquoted and stored in [name] lab and freezer space, *use Protocol 36. Blood Handling Procedure* and *Protocol 37. Serum NTx and Alkphase B Aliquot and Storage* as a guide.

8 ASSESSMENT OF SAFETY

8.1.1 Data

The location of the server is a password protected secured campus UNMC RedCap database server. This server is accessible from the external network, so researchers can design their surveys and provide a link to complete the survey that will work from any Internet-connected device, including mobile devices. This has a secure HTTPS connection. (Please see attached file named: *RedCapServerInfoIRB.Docx*, for more detailed information on the servers and firewall).

Best practices are followed by UNMC IT where the web server and database server are two separate servers and both the web server and database server are securely located behind a firewall. (Please see attached file named: *RedCapServerInfoIRB.Docx*, for more detailed information.).

Exercise logs used by subjects to document their exercises will be stored at individual Y's and then transported by study personnel every 4 weeks for entry into the online data base . On-site ET coordinators at Y's will monitor subject's adherence to exercises by examining subject exercise logs every 2 weeks during the study. Exercise logs must be stored at the Y's because they are used by subjects to document their exercises and by on-site ET coordinators to monitor fidelity of the exercise intervention. Hard copies of data will be kept locked in a file cabinet in the locked office of the study coordinator or the locked office of one of the PIs. Data will be transported in a locked briefcase.

Research data will be linked to subjects by ID code number only. Each subject will be assigned an ID code for use on all study materials. The only link between a subject's name and ID code will be the consent form. A copy of the consent form will be kept in the PI's research office in a locked file separate from other study materials.

As specified by the NIH, subject identifiers will be maintained for 7 years after the study is completed. Funding for the study is requested for 5 years, and study data will be kept for an additional 7 years. All electronic data will be destroyed with the assistance of the ITS and in accordance with UNMC Computer Use and Electronic Information Security Policy NO. 6051

8.1.2 Adverse Events

If a subject is injured or has a medical problem as a direct result of being in this study, the subject has been instructed to immediately contact a member of the study personnel listed at the end of the consent form.

The institution has no plans to pay for any required treatment or provide other compensation. If the subject has insurance, the insurance company may or may not pay the costs of medical treatment. If the subject does not have insurance, or if the insurance company refuses to pay, the subject will be expected to pay for the medical treatment. The subject will be informed that by participating in this research study, she has not given up any of her legal rights.

STUDY OVERSIGHT

The conduct and scientific integrity of this proposed clinical trial will be monitored by a Data and Safety Monitoring Committee (DSMC), comprised of the following persons: [name], PT, PhD, Professor, Division of Physical Therapy Education; [name], [name] of Public Health Biostatistics; [name], [name], School of Allied Health Professions; and [name], PhD, Professor, College of Nursing. The DSMC will audit the implementation of the protocol beginning 6 months after the start of subject accrual. Since this trial is greater than minimal risk, it will be audited every 6 months. Each report will include monitoring of: compliance with informed consent and eligibility requirements, recruitment plan according to protocol, follow-up data collection according to protocol, expected and actual accrual, protocol violations, and patient withdrawals from the study. Per university policy, all serious adverse events (AE) will be reported to the UNMC IRB, the NIH, and to the DSMC Committee within two business days after the investigators have been notified of the AE. The investigators will prepare a summarized report of these above-listed items and submit this report to the DSMC, with access to raw data if needed. A report from the DSMC audit will be sent to the investigators, the UNMC IRB, and NINR-NIH.

The conduct and scientific integrity of this proposed clinical trial will be monitored by a Data and Safety Monitoring Committee (DSMC), comprised of the following persons: [name], PT, PhD, Professor, Division of Physical Therapy Education; [name], [name] of Public Health Biostatistics; [name], [name], School of Allied Health Professions;; and [name], PhD, Professor, College of Nursing.

